Design: As depicted in Figure 1, we have adopted a mixed model, randomized controlled, double-blinded, experimental design that combines the feasibility of a parallel, between-groups approach [Drug condition (morphine vs. placebo saline)] with the statistical power advantages and cost effectiveness of a within subjects approach. Sleep is the within subjects condition [Uninterrupted Sleep (US) vs. Forced Awakenings (FA)]. The US condition is 2, 8-hour nights of undisturbed sleep (US1 and US2), whereas the FA condition involves two consecutive nights (FA1 & FA2) of 8 forced awakenings plus a recovery night (not shown in diagram). Eligibility will be determined by three screening visits, including an adaptation polysomnography (PSG) assessment [Night1 (v3)]. Subjects are randomized (Morphine or Placebo) and will then complete two separate admissions (v4 & v5) at the JHBMC CRU to undergo the US and FA conditions and next day assessments. An optional testing session (see Optional Sleep Pain, Emotions, and Reward Study Procedures, below) will occur in the daytime after US1 and FA1. The order of sleep condition admissions will be counterbalanced and there will be a \geq two week washout period between admissions. The daytime pain testing protocol (Cap/QST & drug) will be performed twice, the day after US2 and the day after two nights of sleep disruption (FA2). The protocol includes blood sampling to quantify inflammatory markers, heat-capsaicin sensitization, quantitative sensory testing (QST), and drug administration. Five QST sessions will be conducted to assess HA and morphine analgesia (1 pre-drug and 4 post-drug; details provided below and in Fig. 3). Morphine/placebo will be administered through subcutaneous injection after the completion of QST1. There will be a 40 minute rest period following morphine/placebo administration to allow for peak analgesic effect to take place. Subsequently QST 2-5 (i.e., rekindling) will be conducted at 40 minute intervals.

Optional Sleep, Pain, Emotions, and Reward Study Procedures

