Screening Visit 2: Subjects will keep standard daily sleep(71-73) and pain diaries(74) for 1 week. Morning entries gather sleep continuity parameters. Evening entries query for daytime pain(63), fatigue, naps, medications, menstruation, and exercise. Subjects will continuously wear an ActiSleep Plus Monitor (or equivalent) wrist accelerometer, which provides objective estimates of circadian rhythm,(75) and sleep continuity(76, 77). Sleep diary and actigraphy data will be reviewed to determine that the sleep, pain, and other eligibility criteria are met. In addition, participants will have the option of providing a saliva sample to be used for future genetic analyses. Should participants accept this option, 1.0 mL of whole unstimulated saliva will be collected by passive drool using a saliva collection aid (e.g., Oragene DNA Self-Collection Kit), stored according to standard specifications. In addition, subjects will have a history and physical exam

Date: 08/30/16 Principal Investigator: [name].

Application Number: NA_00071465

and must test negative for pregnancy via urine pregnancy test (females) and recreational drugs and opioids. A complete blood count test, hepatic and kidney function panel will be performed. Drs. [name], [name], or [name] will make final medical eligibility determinations.

Subjects will be briefly familiarized with the pain testing procedures and capsaicin cream to further help determine eligibility. A thermode will be secured to the forearm with a Velcro strap and will be programmed to emit heat at a constant temperature (e.g., 45°C) for 5 minutes. The thermode will then be removed and .1% capsaicin cream will be applied to the area on which the thermode rested, and will be covered with a raised adhesive patch. Subsequently, the patch and capsaicin will be removed and the skin will be cleaned with an alcohol swab. Participants who find the pain from the capsaicin treatment to be intolerable, or who lack an adequate pain response, will be excluded from further participation in the study. These criteria are in place to avoid causing undue pain (e.g., those whose pain ratings are already quite high would presumably experience even more pain during subsequent quantitative sensory testing over the affected area) and to rule out those whose “baseline” pain scores are too low to assess opioid analgesia.

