Screening Visit 3 [inpatient Clinical Research Unit (CRU)]: Twenty-four hours prior to, and during admission for Visit 3 (v3) and all CRU visits, subjects will refrain from taking analgesics, hypnotics, and other centrally acting (e.g., caffeine) or anti-inflammatory agents. Subjects will undergo a standard PSG, as described below, to rule out occult sleep disorders and provide an adaptation night. Subjects meeting ICSD Criteria(78) for a sleep disorder (e.g. sleep apnea) will be ruled out and referred for clinical care.

Randomization Plan. Subjects passing v3 will remain on the unit and be randomized to receive either morphine or placebo during both of their US and FA admissions (v4 & v5). The Research Pharmacy will generate the randomization list to maintain double-blinding. We will use a dynamic probabilities algorithm with minimization(79, 80) to balance groups on sex, obesity (BMI), and age, since these factors influence pain and inflammation. We will also balance on Chinese ethnicity, due to its association with morphine metabolism(81). To control for sequence effects, we will counterbalance US and FA conditions by randomizing subjects to 1 of 4 sequences: 1) Placebo/US first; 2) Placebo/FA first; 3) Morphine/US first and 4) Morphine/FA first. Subjects randomized to FA first, will remain inpatient for 3 consecutive nights [(v4) FA1, FA2, Recovery]. After two weeks washout, they will complete their US admission(v5). Subjects randomized to the US sequences first will complete the US admission [(v4) US1, US2] followed two weeks later by their FA admission [(v5) FA1, FA2, & Recovery].

Experimental Assessments.

General Inpatient CRU Procedures. To maintain experimental control, subjects will not leave the unit during each admission (v3-5) and will not be permitted to sleep outside their prescribed nocturnal schedule. Staff will continuously monitor, maintain, and regularly document wakefulness. Subjects will wear actigraphs at all times during v3-5 to provide an additional, objective procedural integrity check. Standardized meals and snacks will be provided by the CRU. Breakfast will be served at approximately 7:30 AM. Subjects will continue to complete sleep and pain diaries during v3-5 to provide indices of spontaneous pain and fatigue.

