Questionnaires. Each inpatient evening, subjects will complete the **Stanford Sleepiness Scale**, to measure subjective changes in sleepiness(82) and the Positive Affect Negative Affect Schedule – Extended (83) to measure general affective dispositions and discreet emotions. At baseline only,

participants will complete a battery of questionnaires including the Temporal Experience of Pleasure Scale (84) to measure anticipatory and consummatory anhedonia, the Behavioral Inhibition/Behavioral Activation Scale (85) to measure approach-oriented motivation, the Trait Meta-Mood Scale (86) to assess attention to one's own mood, and the ability to regulate positive and negative moods, and the Monetary Choice Questionnaire to assess delay discounting (87). Research participants will also complete brief computerized cognitive (assessing attention, concentration, and memory) and motivation tasks following the experimental sleep manipulations.

Optional Sleep, Pain, Emotions, and Reward (SPEAR) Study Procedures

Participants will complete several tasks assessing perceptual (e.g., reaction time), emotional, and psychophysiological (e.g., facial electromyography; galvanic skin response) responses to the presentation of emotionally evocative images taken from the standardized and widely used bank of the International Affective Picture System (88). In addition, participants will complete tasks assessing their responses to the presentation of real and hypothetical monetary or food rewards, food reward questionnaires, and a task assessing psychomotor vigilance.

Participants will also undergo quantitative sensory testing (QST) procedures conducted in the parent project to assess responses to heat, pressure, and cold stimuli (e.g., pain threshold, tolerance, intensity). The heat and pressure pain threshold and cold pressor procedures are the same as those conducted in the Mechanisms of Sleep Disruption Hyperalgesia study, and are described in greater detail below. Additionally, heat stimuli will be presented simultaneously with cognitive, emotion and reward-related tasks.

Additionally, participants (N = 15) will have the option to participate in a PET imaging substudy, which will involve an MRI scan and two PET scans (one after each sleep condition).

MRI

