Blood Draws, Pain Testing & Drug Protocol. Figure 3 depicts the timing of blood draws, heat capsaicin procedures, quantitative sensory testing, and drug administration. This protocol will be implemented in the mornings after the US night and the second FA night (FA2). Drs. [name] and [name] have experience conducting all of the pain testing procedures(90-93). Drs. [name], [name], and [name] have extensive expertise studying the effects of opioid agonists(94, 95). All pain testers complete a rigorous training process that includes inter-rater reliability testing ($\kappa > .80$). Participants are permitted to terminate any of the procedures at any time. The following procedures will be conducted in an identical fashion on both visits. All assessments will be conducted by BSMP staff, who will be blind to subject conditions.

Blood Draws & Handling Procedures. Subjects will remain in a semi recumbent position during the procedure. Approximately 30 minutes after Lights On (i.e., wake), the nurse will insert a single port lumen peripheral catheter in an upper extremity vein, contralateral to the arm used for capsaicin testing. A continuous saline infusion at 250cc/h will be maintained. The line will be flushed with saline before and after all blood draws, and will remain installed until the final QST procedure is complete. As shown in Figure 7, seven blood draws will be obtained (3 pre-injection and 4 post-injection). Blood draws 1 and 2 will be obtained approximately 60 minutes apart, prior to the 35 minute heat capsaicin procedure, to provide a resting baseline. After the initial capsaicin procedure, all blood will be drawn prior to each rekindling. Blood will be immediately transported to the Rheumatology Disease Research Core for immediate preparation by the RDRC tech.

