cocaine craving cues, video games, etc (Drobes and Tiffany, 1997; Wong et al, 2006). Thus, [¹¹C]raclopride provides a unique tool for measuring not only D₂ receptors (high and low specific activity), but also for measuring the intrasynaptic dopamine tone (high specific activity alone).

- b. Justification and safety information if FDA approved drugs will be administered for non-FDA approved indications or if doses or routes of administration or participant populations are changed.
N/A
- c. Justification and safety information if non-FDA approved drugs without an IND will be administered.
N/A

7. Study Statistics

- a. Primary outcome variables.

Selection of Independent Variables and Primary Outcomes. The primary independent variable in all analyses is the within-subject comparison of SD versus US. We will also evaluate whether sleepiness (SSS), fatigue (diary), positive and negative affect (PANAS-X) and spontaneous pain (diary) are associated with outcomes and include these variables as covariates in secondary analyses when indicated. Primary outcomes were chosen based on evidence from our prior work and the literature, described above. A summary of primary outcomes by aim is presented in Table 2.

Table 2: Summary of Outcome Measures By Aim

AIM	CONSTRUCT	MEASURE
Aim 1-3	1°HA♦ peripheral sensitization 2°HA♦ spinal sensitization	1°HA-Heat pain threshold (°C), treated skin 2°HA-Surface Area (cm ²), mech. HA untreated skin
Aim 2 & 3	Pain Tolerance	Duration (sec) of hand submersion in 4°C Water
Aim 3	Inflammation - Systemic - Cellular - Genomic - Genomic Signaling	Circulating (plasma) IL-6, TNF-α, IL-1RA** Stimulated & Unstim. PBMC levels of IL-6 & TNF PBMC mRNA conc. of IL-6**, TNF-α**, IL-1β** Stimulated & Unstim. PBMC levels of NF-κB

♦ Heat Capsaicin Testing; ** secondary outcomes

- b. Statistical plan including sample size justification and interim data analysis.

Analytic Plan Hypothesis 1.a. (Sleep disruption enhances HA): We will use multilevel longitudinal mixed effects models to test the null hypothesis that baseline and sleep-deprived indices of 1^o & 2^o hyperalgesia are equal. We will also test for differences in linear time trends by condition.

Hypothesis 2.a. (Sleep disruption diminishes morphine analgesia): Similar models will test the null hypothesis of no effect of sleep deprivation on the analgesic effects of morphine on hyperalgesia and cold pain tolerance. We will also test for differences in linear time trends.

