routinely care for patients with opioid dependence. They have considerable expertise with clinical and research protocols involving opioid administration and naloxone/naltrexone blockade. [name] is also very experienced in these domains and will be available as study physician in the event that both Drs. [name] and [name] are unavailable. Subjects receiving morphine under sleep deprivation conditions will be required to remain on the Unit for a recovery period (overnight) prior to discharge to prevent accidents due to impairment caused by morphine plus sleep deprivation. After the undisturbed sleep condition, subjects will return home the same day, but will not be permitted to drive and instructed not to engage in potentially hazardous activities for the next 12 hours, e.g., cooking, driving, operating heavy machinery, or drinking alcohol or other depressants.

The nursing staff is well trained to assist subjects experiencing side effects such as nausea and emesis. As described, food and drink is limited and restricted prior to injection to minimize these side effects. Subjects will complete the 6-item drug effect VAS and an adjective checklist (36 items), after injection to gather data on frequency and severity of side effects. [name] has used these measures in his opioid pharmacology work to study side-effects of opioid medications. This will be reported regularly to the IRB and our data safety and monitoring committee for review. These measures were specifically designed to capture common and uncommon side effects of morphine and opioid medications.

Sleep Disruption/Deprivation: Because sleep deprivation lowers seizure threshold and may trigger manic episodes in individuals with bipolar disorder, individuals with these conditions are excluded as described. All subjects undergoing sleep deprivation will remain under surveillance on the medical research unit for a recovery night sleep to prevent accidents that might be caused by drowsiness. Because sleep deprivation is a stressor that can impact mood, we have excluded subjects with major psychopathology or acute psychological distress.

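### The sleepiness, affect, fatigue and pain measures planned as correlates and covariates have no stated reading between the second experimental night and the pain test

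*Combined protocol and SAP*

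**What the plan says.** Section 7.a gives four state measures a role in the analysis: "We will also evaluate whether sleepiness (SSS), fatigue (diary), positive and negative affect (PANAS-X) and spontaneous pain (diary) are associated with outcomes". It then allows them as covariates in secondary analyses.

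The reading times are in section 4.a. Under Questionnaires: "Each inpatient evening, subjects will complete the" SSS and the PANAS-X. For the diaries, Screening Visit 2 says "Morning entries gather sleep continuity parameters" and "Evening entries query for daytime pain(63), fatigue, naps, medications, menstruation, and exercise". General Inpatient CRU Procedures carries the diaries into the admissions without restating entry times: "Subjects will continue to complete sleep and pain diaries during v3-5 to provide indices of spontaneous pain and fatigue".

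Blood sampling, heat-capsaicin and quantitative sensory testing (QST) take place on the morning after the last experimental night of each condition. After FA testing the subject stays on the unit for a recovery night (Physiologic Monitoring and Safety). After US testing the subject does not stay: "After the undisturbed sleep condition, subjects will return home the same day" (section 8.b, Administration of Morphine).

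**The concern.** A state measure used to explain or adjust a pain response should describe the subject at the time of the response. On the stated schedule, the reading closest before the FA test is taken before the second night of disruption. The next one comes after the outcome has been measured and the drug given.

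Section 7.a does not say which reading it would use, and each choice has a problem:

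- The evening before the test can miss whatever the second night did to sleepiness, mood, fatigue or pain. A null association could then reassure wrongly.
- The evening of the test day follows capsaicin, heat, cold-pressor testing and injection. Section 8.a lists sleepiness and euphoria among morphine's common side effects, so SSS and PANAS-X that evening may partly reflect the drug. A daytime-pain item may take in the experimental pain. There is also no inpatient US reading to set against it in the within-subject comparison.

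The plan itself treats these states as relevant. Section 8.a names sleepiness and negative mood among the common effects of sleep deprivation, and the opening summary reports that experimental disruption has caused spontaneous pain.

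**Working it through.** **Inputs, all from section 4.a unless stated.** The FA night is an 8-hour (480-minute) opportunity with seven 20-minute awakenings and one of 60 minutes. The catheter goes in about 30 minutes after Lights On. Draws 1 and 2 are about 60 minutes apart, both before the 35-minute heat-capsaicin procedure, and QST1 follows. FA subjects stay a recovery night; US subjects go home on the test day (also section 8.b).

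**1. The plan's own figure.** Time awake per FA night = 7 × 20 + 60 = 200 minutes. Maximum sleep = 480 − 200 = 280 minutes, which agrees with the stated 280.

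**2. Lost sleep opportunity at each point.** Evening before FA1: 0 minutes. Evening before FA2: 200 minutes. Test morning: 2 × 200 = 400 minutes. The last reading before the test follows 200/400 = one half of the manipulation.

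**3. Inpatient evening readings in the two experimental admissions** (the screening night is left out).

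| Evening | FA | US, two nights | US, one night |
|---|---|---|---|
| Before night 1 | Yes; 0 disrupted nights | Yes | Yes |
| Before night 2 | Yes; 1 disrupted night | Yes | Not applicable |
| Between last night and test | None | None | None |
| Test-day evening | Yes; after capsaicin, QST and drug | None (discharged) | None (discharged) |

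The last column is needed because the text conflicts. Design and Randomization Plan give every subject two US nights. Under Experimental Sleep Conditions, the second undisturbed night is added for those who join the optional SPEAR study, and the pain-testing section speaks of a single US night. If subjects outside SPEAR have one US night, their only US reading precedes any experimental sleep.

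**4. Gap between last reading and test.** The evening questionnaires come before lights out, so these are lower bounds. To capsaicin: 8 h + 0.5 h + 1 h = 9.5 h. To QST1: 9.5 h + 35 min = about 10 h. The whole last night lies in between.

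**5. Other instruments that might fill the gap.** The 6-item drug-effect VAS and 36-item adjective checklist are given after injection, for side effects (section 8.b). Their items are not listed, but they come after QST1. The computerized tasks after the sleep manipulation cover cognition and motivation. The ratings during heating are of evoked pain. None is a pre-test reading of the four measures.

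**6. With a reading on the test morning.** Taken between Lights On and catheter insertion, it would precede capsaicin by about 1 to 1.5 h (assuming draw 1 directly follows insertion) and would follow all 400 minutes in FA.

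**The case against.** The strongest reply is that little depends on these measures. They are not outcomes in Table 2. They are not the mediators of Aim 3, which are inflammatory markers, and they do not enter the power calculations. This stands: the point concerns secondary analyses only.

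A reader might infer that the study lacks a manipulation check. The documents do not support that. The plan never assigns SSS or PANAS-X that task. Sleep loss is verified by polysomnography on the experimental nights, by actigraphy and by staff who document wakefulness. These do not measure sleepiness, affect, fatigue or pain, but they do show whether sleep was lost.

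A reader might also infer that no matched FA and US readings exist. If US has two nights, the evening after US1 and the evening after FA1 are matched and precede both drug and capsaicin. They reflect one night, not two.

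The diary part rests on inference. The morning and evening split is described for the screening week, and the inpatient text says only that the diaries continue. The exact wording of the pain item is not given, so it cannot be asserted that the test-day entry is not spontaneous pain, only that it may include experimental pain. A diary entry at home on the US test evening is not excluded, but it would be off the unit and after the drug.

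Finally, the timeline figures could not be checked for questionnaire times. The text describes Figure 3 as covering blood draws, heat-capsaicin, QST and drug, with no questionnaires named.

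**Conclusion.** The point holds as a limit on the secondary analyses in section 7.a. As written, SSS and PANAS-X have no reading between the last experimental night and the pain test in either condition. The same is true of diary pain and fatigue if the screening entry times carry over. The last reading before the FA test reflects half of the planned disruption (200 of 400 minutes) and lies at least about 9.5 hours before capsaicin. The only inpatient reading after both FA nights follows the outcome and the drug and has no inpatient US match. If some subjects have only one US night, their sole US reading precedes any experimental sleep, which makes the problem worse for them.

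A stronger reading, that the main results are compromised, is not supported: none of the primary tests of Aims 1 to 3 uses these variables. No bias in any estimate has been quantified, and the documents give no figures from which to do so. The change is a cheap improvement, worth making because the state at testing cannot be recovered later.

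**What to change.** On each test morning, in both admissions, give SSS, PANAS-X with a momentary time frame, and one current-pain and one current-fatigue rating. Do this after Lights On and before catheter insertion, draw 1 and any heat or capsaicin, at the same point in both admissions. The slot must end before the 30-minute mark, because the catheter is scheduled then and its discomfort could affect pain and mood ratings.

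In section 7.a, name these as the readings for the association and covariate analyses, and state that the test-day evening diary pain entry will not be used as spontaneous pain. State the diary entry times for the admissions, and reconcile the passages on the number of US nights.

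The cost is a few minutes of subject burden on two mornings, mostly with instruments already in use, plus a line in the schedule and a line in section 7.a. The evening readings can stay.

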Heat-Capsaicin and Rekindling Procedures. We will utilize procedures similar to established protocols(96, 97). Heat will be delivered using a computer driven peltier heating element (Medoc TSA II). The procedure involves a 35 minute sensitization period. A 10.24 cm² treatment site, the size and shape of the thermode will be randomly assigned and marked on either a lower or upper, non overlapping surface of the ventral forearm opposite the arm from which blood is drawn. Lower and upper treatment sites will be counterbalanced across admissions. The thermode is secured on the skin with velcro straps and heated at 45°C for 5 minutes. Pain ratings will be collected once every minute on a 0-100 VAS (“no pain”, “most extreme pain imaginable”). An open square, raised adhesive frame patch (internal dimensions same as thermode) is immediately applied to the borders of the treatment site and Capsaicin cream (0.1% Capsaicin)(90) is evenly spread onto the skin and permitted to absorb for 30 minutes. This induces moderate (Mean = 48.25± 27.93), but well tolerated pain. The raised frame prevents spillage or leakage of capsaicin outside the treatment site. Capsaicin is removed, blood draw 3 is obtained, and QST1 is performed as described below. Following morphine/placebo injection and the subsequent 40 minute rest, the treated skin will be rekindled a total of four times at 40 min intervals by heating the treatment site with the thermode at 40°C for 5 min. Following each rekindling episode, a series of QST procedures to quantify 1^o and 2^o Hyperalgesia will be conducted. Studies have demonstrated excellent test-retest stability in hyperalgesia measurements over 4 rekindlings(96, 97, 97). The timing associated with these procedures may vary as a function of experimental demands.

Quantitative Sensory Testing (QST) Procedures. All tests will be conducted in the order described.

Primary Hyperalgesia. Heat-Pain Threshold(HPT_h) will be assessed using an ascending method of limits paradigm prior to application of heat capsaicin, after the 35 minute sensitization period and after each rekindling. The thermode is secured to the treatment site and the temperature gradually increased (rate of rise = .5°C/sec) from a pre-set baseline (31°C), until the subject indicates when

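### Capsaicin treatment site (lower or upper forearm) is counterbalanced across the two admissions but named in no Aim 1 hyperalgesia model, so any site difference stays in the error of the FA-US contrast

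*Combined protocol and SAP*

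**What the plan says.** Under Heat-Capsaicin and Rekindling Procedures (section 4.a), the treatment site "will be randomly assigned and marked on either a lower or upper, non overlapping surface of the ventral forearm", on the arm not used for blood draws. The next statement on site is "Lower and upper treatment sites will be counterbalanced across admissions". Heat pain threshold (1°HA) is taken on the treated skin, and the 2°HA area is mapped around it.

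The Randomization Plan lists the sequences as "1) Placebo/US first; 2) Placebo/FA first; 3) Morphine/US first and 4) Morphine/FA first". The balancing factors are sex, BMI, age and Chinese ethnicity. Site is in neither list.

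Section 7.a states: "The primary independent variable in all analyses is the within-subject comparison of SD versus US". For Hypothesis 1.a, section 7.b plans "multilevel longitudinal mixed effects models to test the null hypothesis that baseline and sleep-deprived indices of" 1° and 2° hyperalgesia are equal across conditions, and adds: "We will also test for differences in linear time trends by condition". The other named variables are sleepiness, fatigue, affect and spontaneous pain; the plan is to "include these variables as covariates in secondary analyses when indicated". No site term appears under Hypotheses 1.a, 2.a or 3.b, or in the description of the power simulations.

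**The concern.** The sponsor treats site as a nuisance factor in the design, but the analysis outline does not carry it forward. Site varies between the same two admissions that form the primary contrast. A participant random effect cannot remove it, because it changes within the participant. A term for admission order cannot remove it either, because site is counterbalanced against admission. If the two sites differ in heat threshold or in mapped area, that difference is left in the residual of the FA-US comparison.

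At stake is the precision of Aim 1, at the smallest effect the plan claims to detect. Site order is also not said to be crossed with sleep order, so by chance more participants could have one site under FA than under US. Under simple random assignment this chance imbalance is not a further harm: it is the same added variance seen from the side of the estimate.

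**Working it through.** **Inputs from the documents.** Section 7.b (Aim 1) gives N=80, standardised outcomes, and power of 80% or greater for effects of 0.40 or greater. It gives neither the Aim 1 alpha nor the correlation between a participant's FA and US outcomes.

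**Inputs assumed.** Two-sided alpha 0.05; power of exactly 80% at 0.40; site difference s of 0.3, 0.5 or 0.7 outcome SDs; the calibrated variance excludes site variance.

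**Step 1: the plan's own figure.** Use the paired normal approximation, power = Φ(0.40 × √80 / SD_d − 1.96), with SD_d² = 2(1 − ρ). The 80% cannot be reproduced from the documents alone, because ρ and alpha are missing. At an effect of 0.40, two-sided:

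- ρ = 0: 71.6% (81.2% one-sided)
- ρ = 0.185: 80.0%
- ρ = 0.3: 85.6%
- ρ = 0.5: 94.7%

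The stated figure is therefore attainable. Solving for exactly 80%: (1.960 + 0.842)/√80 = 0.3132, and SD_d² = (0.40/0.3132)² = 1.631, so ρ is about 0.185.

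**Step 2: add the site difference.** If every participant swaps site, s enters each FA-US difference as +s or -s, and SD_d² = 1.631 + s². If site is drawn independently at each admission, the contribution is +s, 0 or -s with probabilities 1/4, 1/2 and 1/4, so the added variance is s²/2.

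| s | SD_d², all swap | Increase | Power at 0.40 | Effect with 80% power | Power at 0.40, independent draws |
|---|---|---|---|---|---|
| 0 | 1.631 | 0% | 80% | 0.40 | 80% |
| 0.3 | 1.721 | 6% | 78% | 0.41 | 79% |
| 0.5 | 1.881 | 15% | 74% | 0.43 | 77% |
| 0.7 | 2.121 | 30% | 69% | 0.46 | 74% |

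With site in the model, the variance returns to 1.631 and power to about 80% for any s.

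**Step 3: simulation check** (80 pairs, 6,000 runs per scenario, all participants swapping, s = 0.5). The mean estimate was about 0.40 in every scenario, so there is no bias.

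- Simple random site order: power 73.5% without the term and 78.7% with it. The true SD of the unadjusted estimate was 0.153, against about 0.143 at s = 0.
- Exact 40/40 balance: power 75.0% without the term and 79.1% with it. The true SD was 0.144, so it did not rise. Here the loss comes only from an overstated standard error.

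**Step 4: sensitivity to ρ.** At ρ = 0.5 (SD_d² = 1), power at 0.40 is 94.7% with no site effect. It is about 89% at s = 0.5 (variance 1.25) and about 83% at s = 0.7 (variance 1.49). The plan's 80% or greater still holds there.

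**The case against.** The strongest reply is that nothing in the documents shows the site difference to be other than zero. A reader might infer from the eight mapping paths that the wrist restricts a lower-forearm site. The protocol does not support this: the paths start outside the hyperalgesic area and run towards the treated skin, and no distance from wrist or elbow is given. That part of the reply stands, and s is an assumption throughout.

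Second, counterbalancing across admissions does not literally say that each participant swaps. This also stands. Independent draws halve the added variance but do not remove it.

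Third, the calibration reads a bound as an equality and assumes both the alpha and that site variance is not already inside the 1.631. This stands too; the power figures describe one scenario.

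Fourth, Hypothesis 1.a is a short outline, and an unnamed term is not an excluded one. That is fair as a description, but the outline does name its covariates and site is not among them. A term for a factor already controlled by design is better specified before the data are seen.

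Fifth, a heat threshold is recorded before capsaicin and could absorb part of a site effect on 1°HA. No adjustment for it is named, however, and no pre-capsaicin 2°HA area is described.

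Finally, an additive site effect largely cancels in the Aim 2 comparison of pre- and post-drug segments, because both are measured at one site within an admission. Cold pressor tolerance does not use the site. Both points stand and limit the concern to Aim 1 and the pre-drug part of Hypothesis 3.b.

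**Conclusion.** The omission is real, and its consequence is lost precision in the Aim 1 FA-US contrast on 1°HA and 2°HA. Under the calibrated scenario with every participant swapping, the loss is about 2 points of power at s = 0.3, 6 at 0.5 and 11 at 0.7, and smaller with independent draws. It is negligible if the two sites behave alike.

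Two stronger readings are not supported. A reader might infer that the Aim 1 estimate is biased; random assignment and counterbalancing keep it unbiased in expectation. A reader might also infer that the stated 80% is wrong; it is attainable, and at a higher FA-US correlation it survives a site difference of 0.7 SD. The case for acting is that the term costs almost nothing if s is near zero and recovers the lost precision if it is not.

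**What to change.** Add treatment site (lower/upper) as a fixed effect in the Hypothesis 1.a models of 1°HA and 2°HA, and in the Hypothesis 3.b hyperalgesia models that use the pre-drug segment. State whether each participant changes site between admissions. Balance site order against sleep order within each of the four sequences. The term adds little to the pre/post-drug Aim 2 contrast and is not needed for cold pressor tolerance.

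The cost is one degree of freedom per model and one line in the allocation scheme. The site is already assigned and marked at each admission, so it needs only to be kept in the analysis dataset.
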